### 6.2.1. 12-week Induction Period

During the 12-week Induction Period, the actual treatment groups will be derived as:

- **MORF-057 200 mg BID:** If only the MORF-057 200 mg Morning Kit and the MORF-057 200 mg Evening Kit are dispensed and consumed.
- **MORF-057 100 mg QD:** if only the MORF-057 100mg Morning Kit and the MORF-057 Placebo Evening Kit are dispensed and consumed.
- **MORF-057 100 mg BID:** if only the MORF-057 100 mg Morning Kit and the MORF-057 100 mg Evening Kit are dispensed and consumed, and the number of consumed Morning Kits is equal to the number of consumed Evening Kits.
- **Placebo:** If participants received placebo only.

In addition, if a participant randomized to the placebo group receives any dose of MORF-057 by mistake, or if a participant randomized to a MORF-057 dose group receives different MORF-057 dose kits by mistake, he/she will be classified to the MORF-057 dose group in which he/she was treated for the longest duration. In particular,

1. At each visit, the treatment duration of each MORF-057 dose will be calculated as below based on the type of treatment kits dispensed at that visit and the number of consumed capsules of MORF-057 in each dispensed treatment kit.
  - Treatment duration of MORF-057 200mg BID = maximum (the total number of capsules consumed from bottle 1 of MORF-057 200 mg Morning Kit, the total number of capsules consumed from bottle 2 of MORF-057 200 mg Morning Kit, the total number of capsules consumed from bottle 1 of MORF-057 200 mg Evening Kit, the total number of capsules consumed from bottle 2 of MORF-057 200 mg Evening Kit)
  - Treatment duration of MORF-057 100mg BID = minimum (Day\_AM100, Day\_PM100)
  - Treatment duration of MORF-057 100mg QD = absolute (Day\_AM100 - Day\_PM100)

Where,

- Day\_AM100 (the number of days treated with MORF-057 100mg in the morning) = the total number of capsules consumed from the bottle containing MORF-057 of MORF-057 100 mg Morning Kit
- Day\_PM100 (the number of days treated with MORF-057 100mg in the evening) = the total number of capsules consumed from the bottle containing MORF-057 of MORF-057 100 mg Evening Kit

2. The total treatment duration of each MORF-057 dose during the 12-week Induction Period is calculated by summing the treatment durations of that dose across all visits within the period. The actual treatment group assigned to the participant will be the MORF-057 dose group with the longest cumulative duration.

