#### **3.3. Safety Population**

The Safety Population includes all participants who receive at least one dose of study drug (MORF-057 or Placebo).

The safety analysis population will be used for safety analysis. Participants will be analyzed according to the actual treatment received (see Section 6.2 for details). Randomized participants will be excluded from the safety analysis population only if there is documented evidence that participants have not taken any of study drugs (MORF-057 or placebo).

In addition,

- If a participant randomized to the placebo group receives MORF-057 by mistake during the 12-week Induction Period, his/her data for the Induction Period analysis will be included in the MORF-057 dose group in which he/she was treated for the longest duration.
- If a participant randomized to a MORF-057 dose group receives a different MORF-057 dose by mistake during the 12-week Induction Period, his/her data for the Induction Period analysis will be included in the MORF-057 dose group in which he/she was treated for the longest duration.
- If any participants receive a MORF-057 dose different from the one expected in the protocol by mistake during the Maintenance Period/Maintenance Extension Period, their actual maintenance dose group will be based on the MORF-057 dose in which they were treated with the longest duration.

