## 6.2. Determination of the Actual Treatment Groups for Safety Analysis

Enrolled participants will be randomized into 4 treatment groups ([Table 3](#)) and will receive the treatment kits corresponding to the treatment group that they were randomized to, as described in [Table 8](#) below.

During the Induction Period, participants will receive their study drug supplies in Morning Kits and Evening Kits. Each kit includes 2 bottles, each of which contains either MORF-057 or Placebo depending on the kit type. Participants should take 1 capsule from each morning bottle in the morning and take 1 capsule from each evening bottle in the evening for a total of 4 capsules per day.

During the Maintenance Period/Maintenance Extension Period, participants will receive Maintenance Kits with 1 morning bottle and 2 evening bottles. They should take 1 capsule from the morning bottle in the morning and take 1 capsule from each evening bottle in the evening for a total of 3 capsules per day.

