### 6.2.2. Maintenance Period / Maintenance Extension Period

During the Maintenance Period/Maintenance Extension Period, the actual treatment groups will be derived as:

- MORF-057 100 mg BID: if only the MORF-057 100 mg BID Maintenance Kits are dispensed and consumed.
- MORF-057 100 mg QD: if only the MORF-057 100 mg QD Maintenance Kits are dispensed and consumed.
- MORF-057 200 mg QD: if only the MORF-057 200 mg QD Maintenance Kits are dispensed and consumed.

In addition, if a participant receives the MORF-057 Maintenance kits not corresponding to their scheduled dose arm by mistake, he/she will be classified to the MORF-057 dose group in which he/she was treated for the longest duration. In particular,

1. At each visit, the treatment duration of each MORF-057 dose will be calculated as below based on the type of treatment kits dispensed at that visit and the number of consumed capsules of MORF-057 in each dispensed treatment kit.
  - Treatment duration of MORF-057 200mg QD = minimum (the number of capsules consumed from bottle 2 of MORF-057 200 mg QD Maintenance Kit, the number of capsules consumed from bottle 3 of MORF-057 200 mg QD Maintenance Kit)
  - Treatment duration of MORF-057 100mg BID = minimum (Day\_AM100\_Maint, Day\_PM100\_Maint)
  - Treatment duration of MORF-057 100mg QD = absolute (Day\_AM100\_Maint - Day\_PM100\_Maint)

Where,

2. The total treatment duration of each MORF-057 dose during the Maintenance Period/Maintenance Extension Period is calculated by summing the treatment durations of that dose across all visits within the period.. The actual treatment group assigned to the participant for that period will be the MORF-057 dose group with the longest cumulative duration.

- Day\_AM100\_Maint (the number of days treated with MORF-057 100mg in the morning) = the number of capsules consumed from bottle 1 of MORF-057 100 mg BID Maintenance Kit + the number of capsules consumed from bottle 1 of MORF-057 100 mg QD Maintenance Kit
- Day\_PM100\_Maint (the number of days treated with MORF-057 100mg in the evening) = the number of capsules consumed from the evening bottle containing MORF-057 of MORF-057 100 mg BID Maintenance Kit

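### When only one of the two induction kits is wrong, the Section 6.2.1 formulas credit regimens that were not taken and can end in a tie with no tie rule

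*SAP*

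**What the plan says.** Section 3.3 analyses safety by treatment actually received. A participant given the wrong MORF-057 dose in induction is "included in the MORF-057 dose group in which he/she was treated for the longest duration". Section 6.2.1 turns this into formulas. They apply when a placebo participant receives any MORF-057, or "if a participant randomized to a MORF-057 dose group receives different MORF-057 dose kits by mistake".

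For each visit, three durations are computed from capsule counts:

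- 200 mg BID: "Treatment duration of MORF-057 200mg BID = maximum (the total number of capsules consumed from bottle 1 of MORF-057 200 mg Morning Kit", and so on over both bottles of the Morning Kit and both bottles of the Evening Kit.
- 100 mg BID: "Treatment duration of MORF-057 100mg BID = minimum" of the morning and evening 100 mg day counts (Day_AM100, Day_PM100).
- 100 mg QD: "Treatment duration of MORF-057 100mg QD = absolute" difference of the same two counts.

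The durations are summed over visits. "The actual treatment group assigned to the participant will be the MORF-057 dose group with the longest cumulative duration". Neither Section 3.3 nor Section 6.2.1 says what happens in a tie, or where a kit pairing belongs that matches none of the planned regimens.

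Section 6.2 explains that in induction "participants will receive their study drug supplies in Morning Kits and Evening Kits". They are separate items, so one can be wrong while the other is right.

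**The concern.** The maximum gives full 200 mg BID credit when 200 mg was taken in only one half of the day. The absolute difference for 100 mg QD looks only at 100 mg kits, so a 200 mg kit in the other half-day counts there as no drug. When a 200 mg kit is paired with a 100 mg kit, both faults act on the same days.

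The result feeds the induction safety and exposure columns, and induction is the only period with a placebo comparator. For participants randomized to an active dose, Section 4.6.1.2 and the general part of Section 4.9 carry the induction label into the Week 52 and Week 104 exposure and safety columns. A mis-dosed participant's events could therefore stand under a regimen that was never taken, or under a column chosen by the programmer because the rule gives a tie.

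**Working it through.** **Inputs.** The formulas are those of Section 6.2.1 and the kit contents those of Table 8. Induction visits are at Weeks 0, 2, 6 and 12 (Section 1.2), giving intervals of 14, 28 and 42 days. That kits are dispensed at Weeks 0, 2 and 6 is an assumption, because Section 1.4.1 leaves dispensing to the protocol. The section states no numerical result, so there is no figure of the plan's own to reproduce.

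**Step 1: every kit pairing, one 28-day interval, full adherence.** Days credited:

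| AM kit / PM kit | 200 BID | 100 BID | 100 QD | Sum |
|---|---|---|---|---|
| 200 / 200 | 28 | 0 | 0 | 28 |
| 100 / 100 | 0 | 28 | 0 | 28 |
| 100 / placebo | 0 | 0 | 28 | 28 |
| placebo / placebo | 0 | 0 | 0 | 0 |
| 200 / 100, or 100 / 200 | 28 | 0 | 28 | **56** |
| 200 / placebo, or placebo / 200 | **28** | 0 | 0 | 28 |
| placebo / 100 | 0 | 0 | 28 | 28 |

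The first four rows are the planned pairings, and the formulas classify them correctly. For 200 / 100 the maximum is max(28, 28, 0, 0) = 28 and the QD term is |0 - 28| = 28: 56 days credited for 28 treated, split equally between two regimens not taken. For 200 / placebo, 200 mg once daily is counted as 200 mg BID.

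**Step 2: how many single-kit errors are affected.** With 4 groups, 2 kit slots and 2 wrong kits per slot there are 16 possible errors, counting a placebo kit given to an active group as an error.

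- Double-counted (a 200 mg kit with a 100 mg kit): 2 in Group 1, 2 in Group 2, 1 in Group 3, so 5.
- Credited wholly to 200 mg BID without that regimen (a 200 mg kit with placebo): 2 in Group 1, 1 in Group 3, 2 in Group 4, so 5.

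**Step 3: 84-day histories**, fully adherent unless stated. Days are 200 BID / 100 BID / 100 QD:

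| History | Days | Assigned group |
|---|---|---|
| Group 2, 200 mg Morning Kit in Weeks 6-12 | 42 / 42 / 42 | three-way tie |
| Same, with 1, 1 and 3 evening doses missed in the three intervals | 42 / 40 / 41 | 200 BID |
| Same, with 1, 1 and 0 missed | 42 / 40 / 44 | 100 QD |
| Group 1, 100 mg Morning Kits throughout | 84 / 0 / 84 | tie |
| Group 4, 200 mg Morning Kit in Weeks 0-2 | 14 / 0 / 0 | 200 BID |
| Group 2, 200 mg Morning Kit in Weeks 0-2 only | 14 / 70 / 14 | 100 BID, unchanged |
| Group 2, 200 mg Morning Kit in Weeks 2-6 only | 28 / 56 / 28 | 100 BID, unchanged |
| Group 2, both kits 200 mg in Weeks 6-12 | 42 / 42 / 0 | tie, no double count |

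First row: 200 BID = 0 + 0 + 42; 100 BID = 14 + 28 + 0 = 42; 100 QD = 0 + 0 + |0 - 42| = 42. The sum is 126 in an 84-day period. In rows two and three a few missed evening doses decide between two regimens that were not the ones dispensed. Second row: 100 BID = 13 + 27 = 40 and 100 QD = 1 + 1 + 39 = 41. Third row: 100 QD = 1 + 1 + 42 = 44.

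**Step 4: weight of one participant.** With 70 per group, 1/70 = 1.4 percentage points.

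**The case against.** The best defence is that the rule touches only kit mistakes, that the plan reports none of these, and that crediting any 200 mg exposure to the highest dose may be deliberate caution in a safety analysis. Deviations are reviewed before lock (Section 4.7) and data are listed by randomized group (Section 4), so affected participants stay visible. The limited reach is conceded. The caution argument is not supported: the SAP does not state it, the declared principle is longest duration, and it leaves the ties unresolved.

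Several stronger readings should be resisted.

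- *All mis-dispensed days are counted twice.* They are not. Double counting needs a 200 mg kit with a 100 mg kit in the same interval. Swapping both kits together is counted once.
- *Assignment is always pulled to 200 mg BID.* It is not. One history above goes to 100 mg QD, and short errors often leave the group unchanged.
- *Section 6.2.2 proves that the maximum is a slip.* There, "Treatment duration of MORF-057 200mg QD = minimum (the number of capsules consumed from bottle 2" and bottle 3 refers to two evening bottles of one combined maintenance kit. It is not a like-for-like precedent for a rule spanning separate Morning and Evening Kits.
- *The efficacy results are at risk.* Section 3.1 analyses efficacy as randomized.

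**Conclusion.** The point holds for participants with one wrong induction kit. As written, the formulas credit mixed 200 mg and 100 mg pairings in full to two regimens not taken, credit 200 mg with placebo as 200 mg BID, and can produce exact ties that nothing resolves. This is a stated rule that gives wrong results, not merely a missing detail.

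The kit-pair results follow from the formulas alone. The 42/42/42 example also rests on the assumed dispensing weeks and full adherence. The effect is confined to summaries by actual treatment. How many participants are concerned is not given, so the total effect cannot be sized and is probably small. The correction is still worth making, because this rule exists only for such participants and misplaces a good part of them.

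**What to change.** Before database lock and unblinding, replace the three duration formulas in Section 6.2.1 with a rule that credits each interval's days once, according to the AM/PM kit pair dispensed:

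1. 200 mg BID: only days with both 200 mg Morning and 200 mg Evening capsules taken.
2. 100 mg BID: only days with 100 mg Morning and 100 mg Evening capsules taken.
3. 100 mg QD: only days with 100 mg in one half-day and no active drug in the other.
4. Pairings that match no planned regimen (200 mg with 100 mg, 200 mg with placebo): a separate off-regimen duration, not credited to any planned dose.
5. Assign the participant to the planned dose with the longest duration. State a tie rule, for example the randomized group if it is among the tied active doses, otherwise a pre-specified order.
6. List and footnote participants whose longest duration is off-regimen, and state in advance in which column their events appear. This must cover those with no day on a planned active dose, such as the Group 1 and Group 4 histories above.

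The 42/42/42 participant then has 42 days of 100 mg BID and 42 off-regimen days, 84 in all.

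Two simpler repairs fall short. Replacing the maximum by a minimum over the four bottles removes the double count, but gives 200 mg with placebo zero days in every group and leaves 200 mg with 100 mg under 100 mg QD. Letting 200 mg half-days count as 100 mg ones would label 200 mg with 100 mg as 100 mg BID and 200 mg with placebo as 100 mg QD, which merely turns the misclassification downward.

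The cost is SAP wording and a few lines of derivation code, with no new data. The small downside is that a few participants may need a footnoted or separate presentation.

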### 6.2.2. Maintenance Period / Maintenance Extension Period

During the Maintenance Period/Maintenance Extension Period, the actual treatment groups will be derived as:

- MORF-057 100 mg BID: if only the MORF-057 100 mg BID Maintenance Kits are dispensed and consumed.
- MORF-057 100 mg QD: if only the MORF-057 100 mg QD Maintenance Kits are dispensed and consumed.
- MORF-057 200 mg QD: if only the MORF-057 200 mg QD Maintenance Kits are dispensed and consumed.

In addition, if a participant receives the MORF-057 Maintenance kits not corresponding to their scheduled dose arm by mistake, he/she will be classified to the MORF-057 dose group in which he/she was treated for the longest duration. In particular,

1. At each visit, the treatment duration of each MORF-057 dose will be calculated as below based on the type of treatment kits dispensed at that visit and the number of consumed capsules of MORF-057 in each dispensed treatment kit.
  - Treatment duration of MORF-057 200mg QD = minimum (the number of capsules consumed from bottle 2 of MORF-057 200 mg QD Maintenance Kit, the number of capsules consumed from bottle 3 of MORF-057 200 mg QD Maintenance Kit)
  - Treatment duration of MORF-057 100mg BID = minimum (Day\_AM100\_Maint, Day\_PM100\_Maint)
  - Treatment duration of MORF-057 100mg QD = absolute (Day\_AM100\_Maint - Day\_PM100\_Maint)

Where,

2. The total treatment duration of each MORF-057 dose during the Maintenance Period/Maintenance Extension Period is calculated by summing the treatment durations of that dose across all visits within the period.. The actual treatment group assigned to the participant for that period will be the MORF-057 dose group with the longest cumulative duration.

- Day\_AM100\_Maint (the number of days treated with MORF-057 100mg in the morning) = the number of capsules consumed from bottle 1 of MORF-057 100 mg BID Maintenance Kit + the number of capsules consumed from bottle 1 of MORF-057 100 mg QD Maintenance Kit
- Day\_PM100\_Maint (the number of days treated with MORF-057 100mg in the evening) = the number of capsules consumed from the evening bottle containing MORF-057 of MORF-057 100 mg BID Maintenance Kit

### 6.3. Efficacy Outcomes

#### 6.3.1. MCS, mMCS, Partial MCS and Partial mMCS

The MCS, mMCS, and Partial mMCS are composite of subscores as presented in [Table 9](#):

**Table 9: Subscore Components in MCS, mMCS, Partial MCS, and Partial mMCS**

Endpoints	MES	Stool Frequency Subscore	Rectal Bleeding Subscore	PGA
MCS	X	X	X	X
mMCS	X	X	X	
Partial MCS		X	X	X
Partial mMCS		X	X	

MES: Mayo Endoscopic Score; MCS: Full Mayo Clinic Score; mMCS: Modified Mayo Clinic Score; PGA: Physician's Global Assessment

The MCS ranges from 0 to 12; the mMCS and partial MCS range from 0 to 9 and the Partial mMCS ranges from 0 to 6. For all 4 of these composite scores, higher scores indicate more severe disease. Each subscore is described below.

**Stool frequency:** The daily stool frequency score represents each participants' degree of abnormality of the stool frequency.

- 0=Normal number of stools for this participant
- 1=1 to 2 stools more than normal
- 2=3 to 4 stools more than normal
- 3=5 or more stools more than normal

**Rectal bleeding:** The daily bleeding score represents the most severe bleeding of the day.

- 0>No blood seen
- 1=Streaks of blood with stool less than half the time
- 2=Obvious blood (more than just streaks) or streaks of blood with stool most of the time
- 3=Blood alone passed

**MES:** Endoscopy will be used to visualize the mucosa to enable calculation of the MES. The MES reports the worst appearance of the mucosa as visualized by flexible sigmoidoscopy or colonoscopy on a 4-point scale determined centrally by qualified personnel.

- 0=Normal or inactive disease
- 1=Mild disease (erythema, decreased vascular pattern, no friability)
- 2=Moderate disease (marked erythema, lack of vascular pattern, friability, erosions)
- 3=Severe disease (spontaneous bleeding, ulceration)

**Physician's Global Assessment:** The PGA acknowledges the 3 other criteria, the participant's daily recollection of abdominal discomfort and general sense of well being, and other observations, such as physical findings and the participant's performance status.

- 0=Normal
- 1=Mild disease

- 2=Moderate disease
- 3=Severe disease

### 6.3.2. Robarts Histopathology Index (RHI) Score

The RHI is an evaluative index derived from the Geboes Score and calculated by evaluating 4 histologic items:

- Chronic inflammatory infiltrate score (0-3)
- Lamina propria neutrophils score (0-3)
- Neutrophils in epithelium score (0-3)
- Erosion or ulceration score (0-3)

Each item is individually weighted in the RHI formula:

- $RHI = (1 \times \text{chronic inflammatory infiltrate score}) + (2 \times \text{lamina propria neutrophils Score}) + (3 \times \text{neutrophils in epithelium score}) + (5 \times \text{erosion or ulceration score})$

Thus, the total score will be ranged from 0 to 33.

### 6.3.3. Nancy Index (NI)

The NI is determined by evaluating 3 histological items:

- Ulceration (0 or 2)
- Acute inflammatory cells infiltrate (0-3)
- Chronic inflammatory infiltrate (0-4)

An overall grade of NI is 0-4, adjudicated based on the subscores.

### 6.3.4. Geboes Score

The Geboes Score is a stepwise grading system used for the evaluation of microscopic inflammation and histopathologic disease activity in UC. The microscopic appearance of the mucosa is categorized into 6 grades:

- Structural change only (Grade 0)
- Chronic inflammation (Grade 1)
- Lamina propria neutrophils (Grade 2)
- Neutrophils in epithelium (Grade 3)
- Crypt destruction (Grade 4)
- Erosions or ulcers (Grade 5)

Each of these grades has 4 to 5 sub-grades. This scoring system has been converted into a continuous scale that is calculated by adding up the numerical values of the different subscores, yielding a final value between 0 and 22.

### 6.3.5. IBDQ Questionnaire

The IBDQ questionnaire is a psychometrically validated participant reported outcome instrument to assess health-related quality of life (HRQoL) in participants with IBD including UC.

The IBDQ consists of 32 items and is grouped into 4 dimensions:

- Bowel function
- Emotional status
- Systemic symptoms
- Social function

Response to each of the questions is graded from 1 to 7, with the overall score ranging from 32 (very poor HRQoL) to 224 (perfect HRQoL). For the total score and each domain, a higher score indicates better quality of life. A score of  $\geq 170$  corresponds to clinical remission, and an increase of  $\geq 16$  points indicate a clinically meaningful improvement.

## 6.4. SAS Codes for Primary Efficacy Analysis

### Primary SAS Code for Stratified CMH Method

```
proc freq data=adeff;
  table AT_strata * MES_strata *treatment*response/cmh;
run;
```

Where AT\_strata is the previous use of advanced therapy treatment (advanced therapy naïve vs advanced therapy experienced), and MES\_strata is the baseline MES (( $<3$  vs 3)).

## 6.5. The Calculation of Stratified Risk Difference Between Two Groups Using the Cochran-Mantel-Haenszel (CMH) Weights

Suppose that participants are randomly assigned into the active group or placebo group, stratified by K factors ( $K \geq 2$ ):

Strata	Response	Active Group	Placebo	Total
1	Yes	$x_{11}$	$x_{01}$	$x_1$
	No	$n_{11}-x_{11}$	$n_{01}-x_{01}$	$n_1-x_1$
	Total	$n_{11}$	$n_{01}$	$n_1$
2	Yes	$x_{12}$	$x_{02}$	$x_2$
	No	$n_{12}-x_{12}$	$n_{02}-x_{02}$	$n_2-x_2$
	Total	$n_{12}$	$n_{02}$	$n_2$
...				
K	Yes	$x_{1K}$	$x_{0K}$	$x_K$
	No	$n_{1K}-x_{1K}$	$n_{0K}-x_{0K}$	$n_K-x_K$
	Total	$n_{1K}$	$n_{0K}$	$n_K$

Morphic Therapeutic, Inc.  
Study Number: MORF-057-202

Statistical Analysis Plan  
Version 1.0, 16SEP2024

$n_{1j}$  is the number of participants randomized to the active group and  $x_{1j}$  is number of responders in the active group for strata j, and  $n_{0j}$  is the number of participants randomized to placebo and  $x_{0j}$  is number of responders in the placebo group for strata j.

The response rate difference  $\delta_j = p_{1j} - p_{0j}$  between active group and placebo for strata j is estimated by

$$\widehat{\delta}_j = \widehat{p}_{1j} - \widehat{p}_{0j}$$

Where the estimated response rate  $\widehat{p}_{1j} = x_{1j} / n_{1j}$  and  $\widehat{p}_{0j} = x_{0j} / n_{0j}$ .

The overall response rate difference is estimated by the stratified response rate difference using the CMH weights, which is calculated as

$$\widehat{\delta}_w = \sum_{j=1}^K w_j \widehat{\delta}_j$$

where  $w_j = (n_{1j}^{-1} + n_{0j}^{-1})^{-1} / [\sum_{j=1}^K (n_{1j}^{-1} + n_{0j}^{-1})^{-1}]$  is the weight for stratum j with  $\sum_{j=1}^K w_j = 1$ .

The 100  $(1 - \alpha)\%$  confidence interval of the overall response rate difference is given by

$$\widehat{\delta}_w \pm Z_{\alpha/2} \sqrt{\sum_{j=1}^k w_j^2 \widehat{V}(\widehat{\delta}_j)}$$

Where  $\widehat{V}(\widehat{\delta}_j) = (\widehat{p}_{1j}(1 - \widehat{p}_{1j})/n_{1j}) + (\widehat{p}_{0j}(1 - \widehat{p}_{0j})/n_{0j})$  is the estimated variance of the response rate difference in strata j and  $Z_{\alpha/2}$  is the  $(1 - \alpha/2)$  percentile of the standard normal distribution.
